FUNDING ORGANIZATION	National Institutes of Health (NIH) National Institute of Mental Health (NIMH)
NUMBER OF SITES	2
RATIONALE	Depressive disorders are among the most disabling medical conditions worldwide and currently available treatments fall short of addressing this large public health burden. Dysfunction within the brain reward system is emerging as a core feature of depressive disorders, in particular related to deficits in motivation, interest, and response to pleasure (e.g., anhedonia: markedly diminished response to pleasure). Evidences from a series of preclinical studies highlighted the KCNQ subtype of neuronal potassium (K ⁺) channel as a novel target for the treatment of depressive disorders and data from human pilot study showed a reduction in anhedonia and related symptoms, with an increased brain response to reward (as measured by functional magnetic resonance imaging [fMRI]) following treatment with ezogabine, a KCNQ channel opener. Building on these data, the current project will assess reward circuit activity following treatment with ezogabine in depressed patients with anhedonia, and will examine the relationship between change in reward circuit activity and clinically relevant symptom and behavior outcomes.
STUDY DESIGN	This is a phase IIa, randomized, parallel arm, placebo-controlled clinical trial.
PRIMARY OBJECTIVE	To establish target engagement of a KCNQ channel opener (ezogabine) in patients with depressive disorder and anhedonia
SECONDARY OBJECTIVES	To determine if treatment with ezogabine is associated with a reduction in clinical symptoms of depression and anhedonia, and modulation of behavioral responses to reward.
NUMBER OF SUBJECTS	48 randomized across both sites (n=24 in each treatment group)
SUBJECT SELECTION CRITERIA (ABBREVIATED)	Inclusion Criteria: Participants will be aged 18-65 years, with clinically significant anhedonia (Snaitch-Hamilton Pleasure Scale [SHAPS] \geq 20) and a current diagnosis of depressive disorder (Major depressive disorder [MDD], persistent depressive disorder, other specified depressive disorder) according to DSM-5 and at least moderate current illness severity at least moderate (Clinical Global Impression–Severity [CGI-S] Scale \geq 4). Exclusion Criteria: A primary psychiatric diagnosis other than a depressive disorder as defined by DSM-5, neurocognitive disorder, substance use disorder within the past 6 months, contraindication to

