fMRI Task Analysis. Prior to analyzing imaging data, task behavioral data including reaction time (RT) and accuracy in response to flanker stimuli will be analyzed using ANCOVAs (including site, and any potential confounds) to examine main effects and interactions of treatment condition and cue type on reaction time and accuracy. fMRI data will undergo preprocessing using a combination of AFNI, FSL, and Advanced Normalization Tools (ANTs), including despiking, motion correction, alignment to anatomical image (using boundary-based registration), intensity normalization, smoothing (FWHM = 5mm), and warping to standard space. Motion and intensity outliers will be regressed out the data.

Following preprocessing, we will first conduct subject-level (also called ‘first-level’) analyses. As is the norm in the field, subject-level analyses conduct multiple linear regressions for each subject whereby the BOLD signal is predicted from a series of categorical regressors specifying the presence or absence of the conditions of interest across the full timeseries. As an example, in a trial where a cue is shown for 4 seconds followed by an outcome for two seconds, followed by another cue for 4 seconds, the cue regressor would be coded “1” (present) for the first and last 4 timepoints (in seconds) and “0” (absent) for the 2 middle timepoints where the outcome was shown. For each subject, regressions are performed within a standardized neuroimaging analysis software (such as Statistical Parametric Mapping, FSL, or AFNI), producing a single beta weight for each regressor reflecting the relationship between the presence/absence of condition of interest and BOLD signal at each voxel in the brain. For all analyses, the predicted BOLD signal is convolved with a standard hemodynamic response function (hrf) to model the slow rise and fall of the hemodynamic response in the brain. For each subject, the beta weights are then linearly combined to create contrasts (gain > neutral cue contrast, the primary contrast of interest for this study, is the beta weight for gain cue minus beta weight for neutral cue). This contrast represents the mental construct of reward anticipation.

Group level analysis is described in Section 16, Statistical Methods and Consideration.

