1.2.2 Randomization and masking

Patients will be randomized in a 1:1 allocation to ezogabine or placebo. Randomization will be stratified by center balanced by randomly permuted blocks, and treatment code will be allocated through the interactive web response system (IWRS). Randomization will take place only after it has been determined that all study eligibility criteria have been met and the baseline fMRI scan has been obtained.

This is a double-blind, placebo-controlled trial. Site personnel and patients will be blinded to treatment assignment throughout the trial.

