5.4 Efficacy Analysis

5.4.1 Analysis of Primary Endpoint and Determination of Sample Size

The primary endpoint is the change in activation of the bilateral VS, a region of the rewards circuit in the brain, at 5 weeks from randomization. Activation will be measured by fMRI, and beta weights for each subject will be calculated to create a contrast between gain and neutral cues to model reward anticipation as described in the Neuroimaging Methods section of the protocol. To calculate the beta weight for the bilateral VS, the beta weights for the right and left VS will be averaged.

A linear mixed effects model with a single random intercept term will be used to assess the change in activation of the bilateral VS by treatment group. A sample size of 48 provides 85% power to detect a difference in means between groups of 0.8 standard deviations assuming a correlation of 0.6 between a pair of measurements made on the same subject using a two-sided 0.05 significance level test.

Although randomization is stratified by site, the primary endpoint analysis will be of the pooled dataset; secondary analyses will provide site-specific estimates.

No adjustment to the primary analysis will be made for baseline measures that are found to be imbalanced but, if applicable, secondary sensitivity analyses may adjust for any factors that are imbalanced at a significance level below $p = 0.05$. (Altman, 1985) (Peter Peduzzi, 2002) (Senn, 1989) (Senn, Testing for baseline balance in clinical trials, 1993)

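### The primary go/no-go model specifies no site term although randomisation is stratified by centre, so power would be lost if the two sites differ in change from baseline

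*SAP*

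**What the plan says.** SAP 1.2.2 sets the design: "Randomization will be stratified by center balanced by randomly permuted blocks". Protocol 4.1 also stratifies by centre, and there are two sites.

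SAP 5.4.1 names a linear mixed model with one random intercept for change in bilateral ventral striatum activation by treatment group. It then says: "Although randomization is stratified by site, the primary endpoint analysis will be of the pooled dataset", and leaves site to secondary, site-specific estimates. Protocol 16.3 has the same text. Neither section lists the model's fixed effects, and neither mentions a site or site-by-visit term.

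The sample-size statement in SAP 5.4.1 reads: "A sample size of 48 provides 85% power to detect a difference in means between groups of 0.8 standard deviations". It takes a patient's two scans to correlate at 0.6 and sets a two-sided level of 0.05. SAP 3.1 makes this endpoint the only criterion for the go/no-go decision.

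**The concern.** Stratifying by centre balances the arms within each site, so a site difference in outcome cannot move the treatment comparison much. An analysis that leaves out the stratum does not take credit for that. It treats variation between sites as noise, so the calculated standard error exceeds the true variability of the estimate.

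In this trial the relevant quantity is narrow. The contrast of interest is change from baseline, so a fixed difference in signal level between the two scanners drops out with the subject intercept. What does not drop out is a site difference in mean change between the two scans, for example from drift at one scanner or a different case mix. At stake is power for a single decision based on 48 patients. Patients without a follow-up scan are excluded from the primary analysis (Protocol 16.1), and withdrawn patients are not replaced (Protocol 12.3).

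**Working it through.** **Inputs.** From SAP 5.4.1: N = 48, difference 0.8 SD, correlation 0.6, two-sided 0.05, stated power 85%. From the Protocol synopsis: "48 randomized across both sites (n=24 in each treatment group". Three inputs are assumed because the documents do not give them: the 0.8 SD refers to a single measurement; patients split evenly by site, 12 per arm per site; the site difference in mean change, δ, runs from 0 to 1.0 SD of change.

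**Step 1: reproduce the stated power.**
- SD of change = √(2 × (1 − 0.6)) = 0.894.
- Standardised effect = 0.8 / 0.894 = 0.894 SD of change.
- Noncentrality = 0.894 × √(24/2) = 3.098 on 46 df.
- Two-sided power = 85.8%, which reproduces 85%.

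A comparison of post-treatment values only gives 77.4%, and a baseline-adjusted comparison 92.4%; neither matches. The stated power is therefore that of a change comparison with all 48 patients analysed and no site difference in change.

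**Step 2: what an omitted site difference does.** With equal sites and arms balanced within site, δ adds 48 × δ²/4 = 12δ² to the residual sum of squares, in units of the variance of change, on 46 df. The expected residual variance is multiplied by 1 + 12δ²/46:
- δ = 0.25: 1 + 0.75/46 = 1.016, standard error up about 0.8%.
- δ = 0.5: 1 + 3/46 = 1.065, up about 3.2%.
- δ = 1.0: 1 + 12/46 = 1.261, up about 12.3%.

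The true variance of the treatment estimate is unchanged, so the test statistic is too small.

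**Step 3: power and type I error.** Simulated change-score analysis:

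| δ (SD of change) | Pooled power | Power with site | Pooled type I error |
|---|---|---|---|
| 0 | 85.8% | 85.8% | 5.1% |
| 0.25 | 85.4% | about 85.8% | 4.8% |
| 0.5 | 84.4% | about 85.8% | 4.3% |
| 1.0 | 79.8% | about 85.8% | 2.7% |

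Direct numerical integration over the distribution of the pooled statistic gives 85.8%, 85.5%, 84.3% and 79.6% for power and 5.0%, 4.8%, 4.3% and 2.8% for type I error. These agree within 0.2 point. A site difference as large as the planned drug effect (0.8 SD of a single measurement, 0.894 SD of change) gives pooled power of 80.8% and type I error of 3.2%.

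An uneven split makes the loss smaller. At a site difference of 1.0 SD of a single measurement (1/0.894 = 1.118 SD of change), pooled power is 77.9% with a 24/24 split and 80.1% with 36/12.

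**Step 4: cost of the site term when δ = 0.** The same noncentrality on 45 df gives 85.81%, against 85.84% on 46 df: 0.03 point.

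**Step 5: which term is needed.** In one simulated data set with site differences of 1 SD of a single measurement in both level and change, the standard error of treatment-by-visit was 0.319 with no site term, 0.319 with a site main effect only, and 0.264 with site-by-visit. Only the last changes the contrast being tested.

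**The case against.** The absence of a site term is inferred. SAP 5.4.1 lists no fixed effects at all, and pooled could simply mean one combined analysis in place of one per site. That stands as a caution. The opening word of the quoted sentence does suggest a deliberate departure from the stratification, and either way the SAP needs to say how site enters.

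The loss is conditional, and nothing in the documents shows that the sites will differ in change. Separate scanners mainly suggest a level offset, which cancels. The protocol also works against site differences: intensity normalisation (Protocol 9.1.6), and one listed acquisition set, central preprocessing, a common operating procedure and quality tracking (MRI Procedures Appendix). This stands and makes the smaller values of δ the more plausible ones. It does not replace a site term.

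A reader might infer that the go/no-go test is conservative or underpowered as planned. The documents do not support that: at δ = 0 the pooled and site-adjusted analyses perform alike. Nor do they support a biased estimate or a raised risk of a false go, because any error is towards conservatism while arms stay balanced within site.

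A reader might also see an inconsistency with Protocol 9.1.6, where reaction time and accuracy "will be analyzed using ANCOVAs (including site, and any potential confounds"). That contrast is weak. Those analyses are not described as changes from baseline, so a site main effect can matter there, whereas it does nothing for the primary change contrast. Finally, site would matter more in a baseline-adjusted analysis, but SAP 5.4.1 states no such adjustment.

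**Conclusion.** The point holds as a nearly free improvement, with a conditional benefit. The primary model specifies no term for the factor that randomisation is stratified by. The resulting loss is about 0.4 point of power at a site difference of 0.25 SD of change, about 1.4 points at 0.5 SD and about 6 points at 1.0 SD. The last is an assumed upper end, beyond the drug effect the trial is sized to detect.

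The text and the direction of the effect are clear; its size cannot be known from the documents. The figures rest on an even site split, arms balanced within site, all 48 patients analysed, and 0.8 SD read as SD of a single measurement. The stated 85% is correct on its own inputs.

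**What to change.** In SAP 5.4.1 and Protocol 16.3, write out the fixed effects of the primary mixed model: treatment, visit, treatment-by-visit, site and site-by-visit. State that the test is of the treatment-by-visit contrast. A site main effect alone would leave that test unchanged. Keep the site-specific estimates as secondary.

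The cost is one or two lines of wording and one degree of freedom, under 0.1 point of power if the sites do not differ. Protocol section 16 allows modifications in the SAP made before unblinding.

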5.4.2 Secondary Endpoints

All secondary analyses will be performed using the ITT population.

As the secondary fMRI outcomes are exploratory analyses, we will present the mean and 95% confidence interval of the difference in change in activation between treatment groups rather than conducting formal hypothesis testing. As with the bilateral VS, a single beta weight for the bilateral DS will be calculated by averaging the beta weights for the left DS and right DS.

Linear mixed effects models will be used to analyze the anhedonia, depression, and general functioning scales that are collected at multiple time points. Slopes will be estimated with 95% confidence intervals by treatment group. Mean change and 95% confidence intervals by group will be presented for measures collected at baseline and primary outcome only.

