Antiepileptic drugs (AEDs), including ezogabine, have been found to increase the risk of suicidal thoughts or behavior in pooled analyses. Pooled analyses of 199 placebo-controlled clinical trials (mono- and adjunctive-therapy) of 11 different AEDs showed that patients randomized to one of the AEDs had approximately twice the risk (adjusted relative risk 1.8, 95% confidence interval [CI]: 1.2, 2.7) of suicidal thinking or behavior compared to patients randomized to placebo. In these trials, which had a median treatment duration of 12 weeks, the estimated incidence of suicidal behavior or ideation among 27,863 AED-treated patients was 0.43% compared to 0.24% among 16,029 placebo-treated patients, representing an increase of approximately 1 case of suicidal thinking or behavior for every 530 patients treated. There were 4 suicides in drug-treated patients in the trials and none in placebo-treated patients, but the number is too small to allow any conclusion about drug effect on suicide. Suicide ideation and behavior will be monitored during the length of the study through clinical assessments at screening and exit visits, and weekly during the treatment period. The Columbia Suicide Severity Rating Scale (C-SSRS) will also be conducted at each study visit to monitor suicidal ideation and behavior. If, at any point during the clinical trial, a participant will be assessed with a suicidal ideation with any intent or plan, as measured by a C-SSRS score of greater than 3 during the past week and/or with a Global Clinical Impression – Severity Scale (GCI-S) score ≥ 6 (indicating extreme illness severity) or a Global Clinical Impression – Improvement Scale (CGI-I) score ≥ 6 (indicating an extreme worseness of the symptoms), a safety review will be performed by the site PI, or his designee, to determine the appropriate course of action including whether acute intervention is needed and whether it is in the best interests of the subject to continue in the study. For more information, refer to paragraphs 5.3 “Safety evaluations” and section 9 “Study Procedures and Guidelines”.

Other Adverse Effects:

Other side effects include urinary retention, neuropsychiatric symptoms (confusional state, psychotic symptoms, and hallucinations) and withdrawal seizures. To protect participants from these possible side effects the following actions will be completed:

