6.3 Exclusion Criteria

1. A primary psychiatric diagnosis other than a depressive disorder as defined by DSM-5; [co-morbid anxiety disorders (including agoraphobia, generalized anxiety disorder, social anxiety disorder and panic disorder) and Posttraumatic Stress Disorder (PTSD) are allowed];
2. Diagnosis of a major cognitive disorder or evidence of cognitive impairment as assessed by a score of the Mini Mental Status Exam (MMSE) of <24 ;
3. Meets criteria for a substance or alcohol use disorder in the past 6 months;
4. Suicidal ideation with any intent or plan as measured by a Columbia Suicide Severity Rating Scale [C-SSRS] score of greater than 3 during the past month at the time of screening;
5. Female participants who are pregnant, breastfeeding, or may become pregnant, or unwilling to practice birth control during participation in the study;
6. Positive urine toxicology screen for drugs of abuse at the time of screening*;
7. Inability to swallow capsules;

8. Any unstable medical illnesses including hepatic, renal, gastroenterologic, respiratory, cardiovascular (including ischemic heart disease), endocrinologic, neurologic, immunologic, or hematologic disease;
9. Clinically significant abnormalities of laboratory tests, physical examination, or ECG;
10. Positive Hepatitis B surface antigen (HBsAg) and/or Hepatitis C Anti-Hepatitis C virus (HCV) antibody†
11. Moderate to severe renal insufficiency at the time of screening or at any point throughout study participation;
12. Prolonged QT Interval at screening, operationalized as a QTc of > 480 ms;
13. History of abnormal QT prolongation or congenital QT syndrome;
14. Concomitant use of a medication with a known significant risk of QT prolongation;
15. A history of retinal abnormalities (i.e., pigment changes, retinal dystrophy) or findings of retinal pathology on ophthalmological exam at baseline;
16. Presence of a condition or abnormality that in the opinion of the Investigator would compromise the safety of the patient or the quality of the data;
17. Use of any dis-allowed medication according to the study protocol**;
18. Serious and imminent risk of self-harm or violence as determined by the PI;
19. Extreme illness severity as defined by a GCI-S score >6;
20. Any contraindication to MRI including claustrophobia, any trauma or surgery which may have left magnetic material in the body, magnetic implants or pacemakers, and inability to lie still for 1 hour or more;

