3.2.3 Change in Depressive Symptoms

Symptoms of depression will be measured with the Quick Inventory of Depressive Symptomatology, Self-Report (QIDS-SR), the Montgomery-Asberg Depression Rating Scale (MADRS), the Mood and Anxiety Symptoms Questionnaire (MASQ),

and the Columbia-Suicide Severity Rating Scale (C-SSRS). The QIDS, MADRS, and C-SSRS will be collected at baseline (V0) and weekly through the primary outcome assessment (V1 – V5). The MASQ will be collected at baseline (V0) and primary outcome assessment (V5) only.

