4. SAFETY ENDPOINTS

The incidence and frequency of all anticipated and unanticipated serious and non-serious adverse events (AEs) that occur between randomization and study exit (V8) eight weeks after randomization will be determined. Severity/grade and expectedness will be assessed by the study clinician. The Medical Dictionary for Regulatory Activities (MedDRA) system organ class and preferred terms will be recorded for each reported AE.

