5.5 Safety Analysis

All adverse events in this study will be analyzed from the time of randomization. All adverse events will be analyzed using the ITT population.

AEs will be mapped to the MedDRA coding system. The incidence of non-serious AEs and serious AEs will be summarized by System Organ Class, MedDRA Preferred Term and treatment.

The number and percentage of patients with an AE or serious AE will be presented. For the incidence count, a patient will be counted only once for a specific MedDRA Preferred Term, although a MedDRA Preferred Term might be recorded more than once for a particular patient.

The number and rate of each AE will also be presented. Differences in the incidence of individual AEs will be assessed using negative binomial regression with the treatment group as the predictor.

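### A V0–V5 slope is the only C-SSRS-specific analysis in the SAP; it summarises treatment-emergent suicidal ideation poorly, and no C-SSRS safety summary or use of the exit score is planned

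*SAP*

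**What the plan says.** SAP 3.2.3, within the efficacy endpoints, names the QIDS-SR, MADRS and MASQ as depression measures, "and the Columbia-Suicide Severity Rating Scale (C-SSRS") being the fourth. Its timing is: "The QIDS, MADRS, and C-SSRS will be collected at baseline (V0) and weekly through the primary outcome assessment (V1 – V5"). SAP 5.4.2 then says "Linear mixed effects models will be used to analyze the anhedonia, depression, and general functioning scales that are collected at multiple time points" and "Slopes will be estimated with 95% confidence intervals by treatment group". That sentence does not name the C-SSRS; the rule reaches it through 3.2.3, and the SAP gives no other rule for it.

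SAP 4 defines the safety endpoints as "The incidence and frequency of all anticipated and unanticipated serious and non-serious adverse events (AEs) that occur between randomization and study exit (V8"). SAP 5.5 follows suit: "Differences in the incidence of individual AEs will be assessed using negative binomial regression with the treatment group as the predictor". Neither section mentions the C-SSRS or suicidality.

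The protocol treats the instrument mainly as a safety tool. Its synopsis puts suicidality under safety evaluations. Section 2.1 says that antiepileptic drugs, ezogabine included, "have been found to increase the risk of suicidal thoughts or behavior in pooled analyses", and has the C-SSRS done at each visit for monitoring. Section 5.3 uses a score above 3 as a trigger for a safety review. Table 2 places the C-SSRS in the safety block and marks it at study exit, as does the procedure list in section 10.6 (headed Visit 6; the same visit is V8 in protocol section 10 and SAP 4). Section 3.2 also makes suicide ideation an exploratory efficacy measure.

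**The concern.** The C-SSRS grades suicidal ideation and behaviour. Entry excludes anyone with a "score of greater than 3 during the past month at the time of screening", so patients start at 3 or below on that scale. The safety question is then whether ideation or behaviour appears, or worsens, after randomization in either arm. A straight-line trend over six visits does not answer it: the same episode pulls the slope down, leaves it flat or pushes it up according to when it occurs and how long it lasts. An arm slope can also offset new ideation in one patient against falling ideation in another.

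At stake is the group-level reporting of a risk that the protocol itself singles out. C-SSRS worsening that is not recorded as an adverse event would reach the planned C-SSRS results only through this slope. The exit score, taken after the taper, would not reach them at all.

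**Working it through.** **Plan's own figures.** The SAP gives no number for this analysis. The class-risk figures in protocol 2.1 are consistent: 0.43/0.24 = 1.79, against a stated adjusted relative risk of 1.8; 1/(0.0043 − 0.0024) = 526, against a stated figure of about 530.

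**Inputs.** Six weekly assessments, t = 0 to 5 (SAP 3.2.3); slope by arm (SAP 5.4.2); 24 patients per arm (protocol synopsis); safety-review threshold above 3 (protocol 5.3), hence a score of 4 in the example. Assumption: the modelled variable is an ordinal ideation score with 0 for none, because the SAP does not say which C-SSRS score is used.

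**Formula.** The mean of t is 2.5 and the sum of squared deviations is 17.5, so a patient's least-squares slope is Σ(t − 2.5)·y/17.5. The visit weights, times 17.5, are −2.5, −1.5, −0.5, 0.5, 1.5 and 2.5. With complete, balanced data and a random intercept, the arm slope equals the mean of the patients' slopes.

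**Score 4 during the episode, 0 otherwise:**

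| Episode | Calculation | Slope per week |
|---|---|---|
| V1 only | 4 × (−1.5)/17.5 | −0.343 |
| V2 only | 4 × (−0.5)/17.5 | −0.114 |
| V1–V2 | 4 × (−2.0)/17.5 | −0.457 |
| V1–V3 | 4 × (−1.5)/17.5 | −0.343 |
| V1–V4 | 4 × 0/17.5 | 0 |
| V2–V3 | 4 × 0/17.5 | 0 |
| V4 only | 4 × 1.5/17.5 | +0.343 |
| V5 only | 4 × 2.5/17.5 | +0.571 |
| V1–V5 | 4 × 2.5/17.5 | +0.571 |

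An unbroken episode can start and end at any of V1 to V5, which gives 15 patterns. Four have a negative slope, two a zero slope and nine a positive slope. With 0 outside the episode, the sign does not depend on the score level, and the size scales with it.

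**Dropout.** A patient with 0, 4, 4 who then leaves has an own slope of (−1×0 + 0×4 + 1×4)/2 = +2.0 per week.

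**Arm level.** One V1 episode among 24 moves the arm slope by −0.343/24 = −0.014 per week. Four patients with 0, 4, 4, 0, 0, 0 move it by 4/24 × (−0.457) = −0.076 per week.

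**Change score.** V5 minus V0 is 0 for every such episode that resolves before V5, so an endpoint change would miss it too.

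**Counts instead.** The same four patients would show as 4/24 (16.7%). Against 0/24, Fisher's exact p = 0.11. The exact two-sided 95% upper limit for 0/24 is 1 − 0.025^(1/24) = 14.2%. At the cited 0.43%, 24 × 0.0043 = 0.10 cases are expected in an arm.

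**The case against.** The strongest reply is that suicidality is not left out of safety reporting. Adverse events are counted from randomization to V8. Protocol 11.1 counts worsening of a pre-existing condition as an adverse event. Protocol 5.3 sends qualifying events from a safety review into adverse event reporting and names suicidal ideation or behaviour as a possible event at exit. All of this stands. A reader might infer that nothing on suicidality is reported after drug withdrawal; the documents do not support that. What lacks a plan is the exit C-SSRS score, and any C-SSRS worsening not recorded as an adverse event.

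A reader might also infer that the tolerability judgement rests on this slope. No section says so: safety summaries rest on adverse events, the DSMB reviews those at least three times a year, and SAP 3.2 keeps secondary analyses out of the go/no-go decision.

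The generic provisions in SAP 5.1 help somewhat. It presents data by arm, allows counts for categorical variables, defines change from baseline at a given visit (a spike at V1 would be +4 there) and permits a more suitable method if one fails. Protocol 16.4 promises a safety summary by arm. None of these names the C-SSRS or yields a count of patients with emergent ideation.

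Finally, the efficacy placement has a basis in protocol 3.2. Taking the C-SSRS out of the efficacy section would leave that exploratory objective without an analysis. This objection stands, and it is why the remedy is to add a summary.

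**Conclusion.** The gap is real but limited. The only C-SSRS-specific analysis in the SAP can hide or reverse treatment-emergent ideation, and it stops before the exit assessment.

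It would go too far to conclude that early ideation generally scores as improvement. The negative sign requires an episode that starts at V1 or V2, resolves soon enough and occurs in a patient who remains in the study: 4 of 15 patterns, a count of patterns and not a probability. Early ideation that persists to V5, late ideation, and the early-dropout example all read as worsening. A score above 3 triggers a review that may end participation, so the condition of staying in the study matters.

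The size is modest: −0.34 per week for the patient and about −0.014 per week for the arm from one V1 episode. These figures assume an ordinal ideation score, 0 at the other visits, complete data and a random intercept. The consequence is for safety reporting. Individual monitoring, adverse event tables to V8 and the go/no-go decision are unaffected.

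**What to change.** Before unblinding, add a descriptive C-SSRS safety summary to SAP 4 and 5.5, by arm, from randomization to V8:

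- number and percentage with new post-baseline ideation, among patients with none at V0;
- number and percentage with a post-baseline score above 3;
- number and percentage with any suicidal behaviour;
- a shift table of V0 score against worst post-baseline score.

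Show V1–V5 and V8 separately, and give exact 95% confidence intervals. State which C-SSRS score is used. A C-SSRS efficacy summary may stay for the exploratory objective in protocol 3.2, but it should not be the only analysis, and the SAP should say that it is not a safety result.

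The cost is SAP wording and two or three tables from data already collected. With 24 patients per arm the results can only be descriptive.
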